2.6. Sample Size Determination

A total sample size of approximately 195 subjects (approximately 65 per treatment group, randomized 1:1:1, with stratification by systemic corticosteroid use at baseline [yes/no]) is estimated to provide approximately 80% power to detect a difference of 20.4% between each GB004 treatment group and placebo for the primary endpoint of proportion of subjects with clinical remission at PCP Week 12 based on a chi-squared test at an 0.050 two-sided level of significance. This assumes the proportion of subjects with clinical remission at PCP Week 12 is 10% in the placebo group and 30.4% in each GB004 treatment group and a dropout rate by PCP Week 12 of approximately 8%. Subjects with missing clinical remission status at PCP Week 12 will be considered as having not met the primary endpoint.

Using the same sample size assumptions as above for the primary endpoint of proportion of subjects with clinical remission at PCP Week 12 (ie, a difference of 20.4% between each GB004 treatment group and placebo, with a 10% proportion in the placebo group), there will be approximately 80% power for the secondary endpoint of the proportion of subjects with clinical remission at PCP Week 36 based on a chi-squared test at an 0.050 two-sided level of

significance. Subjects with missing clinical remission status at PCP Week 36 will be considered as having not met the endpoint.

3. GENERAL ANALYSIS AND REPORTING CONVENTIONS

Three separate formal statistical analyses will be performed as described in [Protocol Section 9.4](#):

- The PCP Week 12 Analysis will be conducted after all subjects either complete the PCP Week 12 visit or withdraw from the study prior to completion of the PCP Week 12 visit. This analysis will evaluate endpoints at or up through PCP Week 12.
- The PCP Final Analysis will be conducted after all subjects either complete the PCP or withdraw from the study prior to completion of the PCP; This analysis will evaluate all PCP endpoints.
- The OLE Final Analysis will be conducted after all subjects either complete the OLE period or withdraw from the study prior to completion of the OLE period. This analysis will evaluate all OLE endpoints.

This SAP governs the PCP Week 12 Analysis and the PCP Final Analysis.

All analyses will be performed using SAS® System (SAS Institute Inc., Cary, NC) version 9.4 or later.

By-subject listings described in this SAP will be produced for the PCP Final Analysis only.

Categorical variables (ie, those with discrete categories or levels, whether nominal or ordinal) will generally be summarized using descriptive statistics of counts (n) and percentages (%) and will be presented in the format “n (xx.x)”. To ensure completeness, summaries for categorical variables may include all categories, even if no subjects had a value in a particular category. Additionally, for missing data, a category of “Missing” will be presented as needed. Percentages will be rounded to one decimal place. If a count is zero, no percentage will be shown, and if a percentage is 100%, 100.0% will be shown.

Continuous variables will generally be summarized using descriptive statistics: number of subjects with non-missing data (n), mean, standard deviation (SD), median, 25th and 75th percentiles, minimum, and maximum. Descriptive statistics on select measures may also include stool standard errors (SEs) and two-sided, 95% confidence intervals (CIs). In general, rounding rules for reporting continuous descriptive summary statistics are as follows:

- If the original values have 0 or 1 decimal places: mean, median, 25th and 75th percentiles will be reported to one more decimal place than the original values, and SD and SE will be reported to 2 more decimal places than the original values.
- If the original values have 2 or more decimal places: mean, median, 25th and 75th percentiles, SD, and SE will all be reported to 3 decimal places.

Original values include both reported raw data values and derived values. In the case of derived values, an appropriate determination for precision will be made based on the reported raw data values used for derivation. Minimum and maximum will always be reported to the same number of decimal places as the original values, up to a maximum of 3 decimal places. Percent change

from baseline will be reported to 1 more decimal place than change from baseline, up to a maximum of 3 decimal places.

Efficacy results will be summarized by various measures, including, but not limited to, absolute differences in proportions, odds ratios (ORs), least squares (LS) means, differences in LS means, SEs, p-values, and two-sided, 95% CIs. Absolute differences in proportions and corresponding CIs will be reported to 1 decimal place. ORs and their corresponding CIs will be reported to 3 decimal places. Least squares means and differences in LS means and their corresponding CIs and SEs will be reported per the rules above, with the CIs following the same rounding rules as the corresponding means. P-values will be reported to 4 decimal places, with values less than 0.0001 displayed as < 0.0001 and values greater than 0.9999 displayed as > 0.9999. All statistical hypothesis testing for efficacy endpoints will be at an 0.050 two-sided level of significance.

Summaries of subject disposition, major protocol deviations, demographic and other baseline characteristics, UC treatment history, and concomitant UC background medications at baseline will be presented by randomized treatment group and will also include an overall column combining all treatment groups. Summaries of medical history and prior medications will be presented by actual treatment group and will include an overall column combining all treatment groups. Summaries of concomitant medications, duration of study treatment, compliance, prescribed dose modifications, and time on study will be presented by actual treatment group and will also include a total GB004 column combining both GB004 treatment groups. Efficacy tables will be presented by randomized treatment group only. Safety tables will be presented by actual treatment group and, in general, will also include a total GB004 column combining both GB004 treatment groups.

When appropriate, sorting of non-ordinal categorical variables in tables will be based on decreasing frequency within the overall column. In general, adverse event (AE) tables that are displayed by system organ class (SOC) and preferred term (PT) will be sorted by the internationally agreed order for SOC, and by decreasing incidence and then alphabetically for PT within SOC in the total GB004 column. Otherwise, AE tables, when applicable, will be sorted by decreasing incidence within the total GB004 column.

In general, assessments at the PCP Day 1 visit are to be performed prior to the first dose of study treatment at the PCP Day 1 visit. Therefore, the baseline value is defined as the last non-missing value on or before the first dose of PCP study treatment, unless otherwise specified.

For analyses of change from baseline and percent change from baseline parameters, only subjects with a baseline value and at least one post-baseline value will be included. For maximum post-baseline analyses, only subjects with at least one post-baseline value will be included. Analyses of shift from baseline, outliers, and abnormalities will generally be based on the number of subjects at risk.

Values with “<” or “>” signs will be analyzed without the signs in tables and figures. In by-subject data listings, values will be reported as collected with the sign.

Dates in by-subject data listings will be displayed as yyyy-mm-dd (eg, 2021-01-24). In general, by-subject data listings will be sorted by treatment group, subject number, and study day.

3.1. Determination of Data for Inclusion in Placebo-Controlled Period Analyses

In general, statistical analyses described in this SAP will be performed separately for the PCP Week 12 Analysis and for the PCP Final Analysis. The PCP Week 12 Analysis is intended to analyze endpoints at or up through PCP Week 12, and the PCP Final Analysis is intended to evaluate all PCP endpoints. Therefore, a determination of study data to be included in the PCP Week 12 Analysis and the PCP Final Analysis is required.

3.1.1. Placebo-Controlled Period Week 12 Analysis

For subjects who consent only to version 1.0 of the protocol, which includes only a 12-week placebo-controlled treatment period, all data reported will be included in the PCP Week 12 Analysis.

For subjects who consent to version 2.0 of the protocol, which includes a 36-week placebo-controlled treatment period and a 24-week OLE treatment period, data to be included in the PCP Week 12 Analysis will generally be dependent upon whether a subject continues in the PCP beyond PCP Week 12 as follows:

- For subjects who withdraw from the PCP prior to PCP Week 12 and subjects who withdraw from the PCP at PCP Week 12 without transitioning into OLE, all data reported, including data from the PCP Follow-up visit, will be included in the PCP Week 12 Analysis.
- For subjects who withdraw from the PCP and transition into the OLE at PCP Week 12, all data up through the date and time (where ascertainable) of first dose of OLE study treatment will be included in the PCP Week 12 Analysis.
- For subjects who continue in the PCP beyond PCP Week 12, all data reported up through and including PCP Week 12 will be included in the PCP Week 12 Analysis.

3.1.2. Placebo-Controlled Period Final Analysis

For subjects who consent only to version 1.0 of the protocol, all data reported will be included in the PCP Final Analysis.

For subjects who consent to version 2.0 of the protocol, data to be included in the PCP Final Analysis will generally be dependent on whether a subject is dosed in the OLE as follows:

- For subjects not dosed in the OLE, all data reported will be included in the PCP Final Analysis.
- For subjects dosed in the OLE, all data up through the date and time (where ascertainable) of first dose of OLE study treatment will be included in the PCP Final Analysis.

3.2. Analysis Visit Windowing

Subjects do not always strictly adhere to the visit schedule timing in the protocol. Therefore, the designation of analysis visits (or timepoints) will generally be based on the actual day of evaluation relative to the date of first dose of PCP study treatment (Day 1), rather than the

nominal visit, for analyses conducted by visit or analyses conducted at a visit, unless otherwise stated.

Mutually exclusive analysis visit windows containing no gaps will generally be utilized to assign analysis visits corresponding to scheduled post-baseline visits specified in the protocol and will be based on data from both scheduled and unscheduled visits/assessments. Analysis visits will be assigned by using a windowing scheme as described below.

The target day for analysis visits for the PCP Week 2, 4, 8, 12, 18, 24, 30 and 36 visits is the week number multiplied by 7 plus 1 (eg, target day for the PCP Week 2 analysis visit is Day 15). The protocol-specified Follow-up visit in the PCP will have an analysis visit designation of Week 40 (Follow-up), and therefore, the week number for the Follow-up visit will be considered to be Week 40 for analysis visit windowing (ie, target day of 281).

The upper bound of the baseline analysis visit window is Day 1 (up to and including the time of first dose of PCP study treatment for assessments with time collected), and the lower bound of the first post-baseline visit window is Day 1 after the time of first dose of PCP study treatment (for assessments with time collected) or Day 2 (for assessments without time collected). For all other lower and upper bounds of analysis visit windows, with the exceptions noted below, windows will end at the midpoint between scheduled visit timepoints, with the midpoint itself assigned to the latter visit window.

The upper bound of the PCP Week 12 analysis visit window for assessments collected per the protocol SoA at both the PCP Week 12 and PCP Week 18 visits and for the PCP Week 12 flexible sigmoidoscopy with biopsy will be Day 107 (allowing for a 22-day upper analysis visit window after the target day of Day 85). This upper analysis visit window incorporates the protocol-specified 5-day visit window for the PCP Week 12 visit, the additional protocol-specified 14-day allotment to allow for any delay in endoscopy assessment due to a pandemic (eg, Coronavirus Disease 2019 pandemic) or other global health emergency, and the protocol-specified requirement that the PCP Week 12 visit be conducted in-clinic within 3 days post-endoscopy.

Similarly, the upper bound of the PCP Week 36 analysis visit window for assessments collected per the protocol SoA at both the PCP Week 36 and PCP Follow-up visits and for the PCP Week 36 flexible sigmoidoscopy with biopsy will be Day 275 (allowing for a 22-day upper analysis visit window after the target day of Day 253). This upper analysis visit window incorporates the protocol-specified 5-day visit window for the PCP Week 36 visit, the additional protocol-specified 14-day allotment to allow for any delay in endoscopy assessment due to a pandemic (eg, Coronavirus Disease 2019 pandemic) or other global health emergency, and the protocol-specified requirement that the PCP Week 36 visit be conducted in-clinic within 3 days post-endoscopy.

If a subject's last assessment is after the date of first dose of PCP study treatment but prior to the first scheduled post-baseline visit/assessment, that assessment will be assigned to the first post-baseline scheduled visit. If two or more assessments occur in the same visit window, the assessment closest to the target visit day will be selected for inclusion in the analysis. If multiple assessments are equally close to the target visit day, then the latest assessment will be selected for inclusion in the analysis. If multiple assessments occur on the same day, the average of these assessments will be used for analysis (for evaluations with continuous values), excluding

analyses evaluated at any time post-baseline (eg, maximum post-baseline, shift from baseline, abnormality, and outlier analyses).

Further details regarding analysis visit windowing for efficacy endpoints are described in [Section 8.5.1](#).

3.3. Standard Calculations

Standard calculations are described as follows:

Age:

Either date of birth or age at informed consent (as an integer) is collected in the IRT system for a given subject. If date of birth is collected, age at time of first dose of PCP study treatment will be calculated in years as $[(\text{date of first dose of PCP study treatment} - \text{date of birth} + 1)]/365.25$, rounded down to the nearest integer. If age at informed consent is collected, age at time of first dose of PCP study treatment will be set equal to the reported age at informed consent.

Change/Percent Change from Baseline:

Change from baseline will be calculated as: Value at post-baseline visit – value at baseline.

Percent change from baseline will be calculated as: $(\text{Change from baseline}/\text{value at baseline}) * 100\%$.

If the value at baseline is 0, percent change from baseline will be missing.

Study Day:

Study day will be calculated as follows:

Date of assessment – Date of first dose of PCP study treatment, where date of assessment is prior to the date of first dose of PCP study treatment

Date of assessment – Date of first dose of PCP study treatment + 1, where date of assessment is on or after the date of first dose of PCP study treatment.

Duration:

Where needed, the duration between two dates Date1 and Date2 will be calculated as follows:

Date2 – Date1 + 1, when expressed in days

$(\text{Date2} - \text{Date1} + 1)/7$, when expressed in weeks.

3.4. Considerations Related to the COVID-19 Pandemic

Screening of subjects for this study began in September 2020. As such, this study's conduct may be affected by the global Coronavirus Disease 2019 (COVID-19) pandemic. Prospectively specified measures to allow for adjustment in study conduct due to the COVID-19 pandemic (eg, measures addressing missed visits, alternative methods of performing study procedures, and alternative methods of supplying IP to subjects), with the objectives of maximizing subject monitoring, data collection, and endpoint ascertainment, are described in [Protocol Appendix 9](#).

Several regulatory authorities have issued guidances related to clinical trial conduct and associated methodological issues related to the effect of the COVID-19 pandemic, including, but not limited to, the Food and Drug Administration (FDA) ([FDA, 2020a](#), Guidance on Conduct of Clinical Trials of Medical Products during COVID-19 Pandemic and [FDA, 2020b](#), Statistical Considerations for Clinical Trials During the COVID-19 Public Health Emergency) and European Medicines Agency (EMA) ([EMA, 2021](#), Guidance on the Management of Clinical Trials during the COVID-19 (Coronavirus) pandemic, Version 4 and [EMA, 2020](#), Points to consider on implications of Coronavirus disease (COVID-19) on methodological aspects of ongoing clinical trials).

Potential effects on conduct of this study related to the COVID-19 pandemic include, but are not limited to, the following: subject discontinuation of study treatment and/or withdrawal from study; temporary site closure; inability or reduced ability for subjects to continue on IP due to disruptions in IP dispensing; extending protocol-defined windows for visits to enable endpoint ascertainment, which is addressed in [Protocol Appendix 9](#); missed visits or missed assessments; and alternative ascertainment methods (eg, remote ascertainment via a telephone visit or virtual visit) used in visits or assessments for collection of data contributing to efficacy and/or safety endpoints.

A determination will be made at the end of study if additional statistical analyses are warranted, should conduct of the study have been affected by the COVID-19 pandemic to a substantial degree. This determination may be made by assessing various aspects, such as the number of subjects with missed visits or assessments for reasons related to the COVID-19 pandemic, the number of subjects with alternative ascertainment methods used in visits or assessments, the number of subjects who discontinued study treatment and/or withdrew from the study for reasons related to the COVID-19 pandemic, and the number of subjects for whom IP dispensing was affected (eg, interruption in IP dispensing or alternative methods for supplying IP) for reasons related to the COVID-19 pandemic. Summary tables and/or by-subject data listings may be provided as part of this assessment.

If the determination of this assessment is that conduct of the study was substantially affected by the COVID-19 pandemic, additional statistical analyses may be undertaken to enable an understanding of the potential impact of the COVID-19 pandemic on study results, particularly in the scenario of statistically significant results for the primary and/or secondary endpoints.

A non-exhaustive list of examples of such additional statistical analyses is as follows:

- Analysis of compliance:
 - By subgroup of subjects for whom IP dispensing or accountability was affected for reasons related to the COVID-19 pandemic versus subjects for whom IP dispensing was not affected;
- Analyses of primary and select secondary efficacy endpoints:
 - By subgroup of subjects whose study participation was affected by the COVID-19 pandemic versus subjects whose study participation was not affected;
 - Excluding only data that is missing for reasons related to the COVID-19 pandemic (but including imputation of data missing for other reasons); and

- By subgroup of subjects who had an alternative method of collection for an assessment contributing to a particular endpoint (eg, mobile endoscopy) versus subjects who did not have an alternative method of collection
- Analysis of AEs:
 - Incidence of AEs by subgroup of subjects whose study participation was affected by the COVID-19 pandemic versus subjects whose study participation was not affected;
 - Incidence of AEs that were collected via an alternative method versus incidence of AEs that were not collected via an alternative method
- Analysis of laboratory values:
 - By subgroup of subjects whose study participation was affected by the COVID-19 pandemic versus subjects whose study participation was not affected; and
 - Excluding values resulting from local collection due to reasons related to the COVID-19 pandemic.

4. ANALYSIS POPULATIONS

4.1. All Enrolled Population

The all enrolled population will include all subjects with a non-missing date of informed consent. The all enrolled population will be utilized for analysis of subject disposition.

4.2. PCP Intent-to-Treat Population

The PCP intent-to-treat (ITT) Population will include all subjects who are randomized and receive at least 1 dose of PCP study treatment. Subjects will be grouped according to their randomized treatment, regardless of the treatment actually taken or received.

The PCP ITT population will be used for analyses of major protocol deviations, demographic and other baseline characteristics, UC treatment history, concomitant UC background medications at baseline, and efficacy.

4.3. PCP Safety Population

The PCP safety population will include all subjects who receive at least 1 dose of PCP study treatment, with subjects grouped according to their actual treatment.

Determination of actual treatment will be as follows. Subjects who are randomized to placebo or GB004 480 mg QD will be grouped according to their randomized treatment group, except for cases where a subject receives and takes IP from one or more misdispensed IP bottle(s) (defined as an IP bottle which was not assigned to the subject by the IRT system) whose treatment group identity differs from randomized treatment. In such cases, subjects randomized to placebo will be grouped in the GB004 480 mg QD or GB004 480 mg BID treatment groups only if GB004 was actually taken, with treatment grouping determined according to the greater frequency (QD or BID) of GB004 actually taken based on study treatment accountability data, and subjects

randomized to GB004 480 mg QD will be grouped in the GB004 480 mg BID treatment group only if GB004 was actually taken BID based on study treatment accountability data.

The PCP safety population will be utilized for analyses of medical history, prior and concomitant medications, duration of study treatment, compliance, prescribed dose modifications, time on study, and safety.

5. STUDY SUBJECTS

5.1. Disposition of Subjects

The disposition of subjects will be summarized. Disposition and screen failure data will also be presented in by-subject data listings. In addition, a listing of the randomization scheme will be presented.

5.1.1. Placebo-Controlled Period Week 12 Analysis

The following counts and percentages of subjects will be summarized:

- Screened
- Screen failures, including screen failure reasons
- Randomized
- Randomized in Error, defined as randomized subjects who have any inclusion/exclusion criteria not met, including those specific inclusion/exclusion criteria not met
- Treated
- Analysis populations (All Enrolled, PCP ITT, and PCP Safety)
- Protocol version of informed consent (Version 1.0 or Version 2.0)
- Completed PCP Week 12 on study treatment
 - Met protocol-defined UC disease activity criteria at PCP Week 12
- Did not complete PCP Week 12 on study treatment, including reasons for study treatment discontinuation prior to PCP Week 12
- Completed PCP Week 12
- Did not complete PCP Week 12, including reasons for withdrawal prior to PCP Week 12

If a subject who consented to version 2.0 of the protocol did not complete study treatment in the PCP, a determination of whether the subject completed PCP Week 12 on study treatment will be made based on the subject's date of last dose of study treatment in the PCP relative to the subject's nominal PCP Week 12 visit date or relative to the target day of Day 85 for the PCP Week 12 visit if the nominal PCP Week 12 visit date is missing.

Similarly, if a subject who consented to version 2.0 of the protocol did not complete the PCP, a determination of whether the subject completed PCP Week 12 will be made based on the subject's last assessment date relative to the subject's nominal PCP Week 12 visit date or relative to the target day of Day 85 for the PCP Week 12 visit if the nominal PCP Week 12 visit date is missing.

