4.1.1. Placebo-Controlled Period (36 weeks)

After signing an informed consent form (ICF), subjects will be screened for study eligibility over a Screening period of up to 5 weeks. During the Screening period, subjects will capture stool frequency and rectal bleeding symptoms in a provided electronic diary (eDiary) on a daily basis. Flexible sigmoidoscopy or colonoscopy will be performed at screening. Subjects not meeting the eligibility criteria will be deemed screen failures and will not continue participation in the study.

On Day 1/Week 0, eligible subjects will be randomized 1:1:1 to receive the following treatments for 36 weeks:

- GB004 480 mg BID
- GB004 480 mg once daily (QD)
- Placebo

Randomization will be stratified by systemic corticosteroid use at baseline (yes/no).

All subjects will dose investigational product (IP) BID to maintain the blind (for details refer to Section [6.1](#)). The first dose of IP will be administered in the clinic on Day 1/Week 0 with food.

All subsequent doses will be taken at home with food, with the exception of the morning doses at

the Week 2, 4, 8, 12, and 36 visits where IP will be administered in the clinic, with food, after predose blood collection as specified in the Schedule of Activities (SoA) in Section 1.3.1 – PCP.

After initiation of IP on Day 1/Week 0, subjects will return to the clinic and will be evaluated as specified in the SoA, see Section 1.3.1. A flexible sigmoidoscopy with biopsies will be performed at the PCP Week 12 and Week 36 visits (and at the Unscheduled UC Disease Activity Criteria Assessment visit(s) and at the Early Withdrawal from Study visit, if applicable).

Subjects who permanently discontinue IP without enrolling in the OLE will be encouraged to continue in the PCP and will complete the Early Discontinuation of IP visit at the time of IP discontinuation and then complete the remaining PCP study visits per the SoA. At subsequent visits, all study procedures will be completed per the SoA excluding dispensation/return and accountability of IP.

Subjects who withdraw from the PCP without enrolling in the OLE, regardless of the reason, will be requested to return to the clinic to complete the Early Withdrawal from Study visit and will be asked to return for a Follow-up visit approximately 4 weeks after their last dose of IP to assess safety.

For dose modifications refer to Section 6.5.1.

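### SAP 5.1.1 can report a subject who withdrew before Week 12 as a Week 12 completer, because the last assessment date it relies on does not exclude the safety Follow-up visit

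*SAP*

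**What the plan says.** The Week 12 disposition summary in SAP 5.1.1 reports two kinds of completion, each with reasons for those who did not complete: reaching Week 12 on study treatment, and reaching Week 12 in the study.

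For study completion, the derivation applies "if a subject who consented to version 2.0 of the protocol did not complete the PCP". In that case "a determination of whether the subject completed PCP Week 12 will be made based on the subject's last assessment date", and the comparator is when the nominal Week 12 visit took place. The fallback comparator reads: "relative to the target day of Day 85 for the PCP Week 12 visit if the nominal PCP Week 12 visit date is missing". For completion on treatment, the parallel determination is "based on the subject's date of last dose of study treatment in the PCP". SAP 5.1.2 repeats the Week 12 counts in the PCP Final Analysis.

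Four other places bear on how the date will be read:

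- SAP 3.2: the target day "is the week number multiplied by 7 plus 1", so Week 12 is Day 85.
- Protocol 4.1.1: subjects who withdraw from the PCP without entering the open-label extension will be "asked to return for a Follow-up visit approximately 4 weeks after their last dose of IP to assess safety". The schedule in Protocol 1.3.1 allows this visit 3 days early to 7 days late.
- SAP 3.1.1: for subjects who withdraw before Week 12, "all data reported, including data from the PCP Follow-up visit, will be included in the PCP Week 12 Analysis".
- SAP 2.6: the sample size assumes "a dropout rate by PCP Week 12 of approximately 8" percent.

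**The concern.** A subject who withdraws before Week 12 normally has no Week 12 visit, so the comparison falls back to Day 85. If that subject returns for the safety visit, the last assessment is about 28 days after last dose and can fall after Day 85. The rule then returns completed for someone who left the study and was seen only once more, for safety.

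This matters for two reasons. The Week 12 withdrawal count is what a reader would compare with the 8% planning assumption. The protocol also encourages subjects who stop treatment to stay for the remaining visits, so the table should separate those who stopped treatment but were retained from those who left. Under this rule, some who left look retained, and their withdrawal reasons drop out of the Week 12 non-completer line.

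**Working it through.** **The plan's own figure first.** The only stated result that uses Week 12 dropout is the power in SAP 2.6: 65 per group, 10% versus 30.4%, two-sided 0.050, 8% dropout. With n = 65 × 0.92 = 59.8 per group and mean proportion 0.202:

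z = [0.204 × √59.8 − 1.96 × √(2 × 0.202 × 0.798)] / √(0.10 × 0.90 + 0.304 × 0.696) = (1.578 − 1.113) / 0.549 = 0.846, giving power 0.801.

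The stated 80% reproduces and is not in question.

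**Does the last assessment include Follow-up?** SAP 5.1.1 does not define the term. Two other sections indicate that it does. SAP 3.1.1 brings early withdrawers' Follow-up data into the Week 12 Analysis. SAP 7.4 runs time on study to the last PCP assessment for these subjects. Its Week 12 categories go up to at least 16 weeks (12 plus the 4-week Follow-up), and its Final Analysis categories name the Week 40 Follow-up window.

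**Threshold.** Week 12 target = 12 × 7 + 1 = Day 85. Earliest last-dose day that puts an attended Follow-up on or after Day 85:

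| Follow-up after last dose | Earliest last-dose day | Days affected, of Days 1 to 84 |
|---|---|---|
| 25 days (3 early) | 85 − 25 = 60 | 25 (29.8%) |
| 28 days | 85 − 28 = 57 | 28 (33.3%) |
| 35 days (7 late) | 85 − 35 = 50 | 35 (41.7%) |

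Example: last dose and Early Withdrawal visit on Day 60, Follow-up on Day 88. Since 88 is past 85, the subject is classed as a completer.

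**Illustrative size.** Assumptions, none given in the documents: 8% of 195 = 15.6 dropouts; last-dose days uniform over Days 1 to 84; dosing stops at withdrawal; none has a Week 12 visit; all consented to version 2.0; on or after Day 85 counts as complete. With attendance a and Follow-up at 28 days, the number moved is 15.6 × (28/84) × a:

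| Follow-up attendance | Moved to completed | Reported dropout |
|---|---|---|
| 100% | 5.2 | (15.6 − 5.2)/195 = 5.3% |
| 50% | 2.6 | (15.6 − 2.6)/195 = 6.7% |
| 25% | 1.3 | (15.6 − 1.3)/195 = 7.3% |

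At full attendance, the Follow-up window moves the first row between 4.7% (Day 50 threshold) and 5.6% (Day 60). If last doses on Days 80 to 84 are set aside because they lie inside the ±5-day Week 12 window, the share is 23/79 = 29.1%. That moves 4.5 subjects and gives (15.6 − 4.5)/195 = 5.7%.

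**Downstream.** SAP 7.4 and 9.1 also split version 2.0 subjects by whether they withdrew at or before Week 12. If the same derived status is used there, a misclassified subject with no Week 12 visit has time on study set to 85 days and adverse events counted only through Day 85, although SAP 3.1.1 includes all data from early withdrawers. Whether this happens depends on programming.

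**The case against.** The strongest reply is that this is an undefined term, not an error. SAP 5.1.1 gives neither a definition of last assessment nor the direction of the comparison. SAP 3.1.1 itself describes subjects who withdrew before Week 12 and have Follow-up data, so its authors evidently saw the two as compatible. That is fair as to intent. But a programmer must code the written rule, and the use of Follow-up data in SAP 3.1.1 and 7.4 points to counting that visit.

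A second reply is that little is hidden. Everyone affected has a last dose before Day 85 and so appears, with a reason for stopping treatment, in the on-treatment line. The Final Analysis adds overall PCP withdrawal with reasons, and there are by-subject listings. This stands, and it confines the problem to the Week 12 study-completion and withdrawal-reason counts. It does not make those counts right.

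Some stronger readings are tempting but not supported:

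- A reader might infer that these subjects all have missing Week 12 status and are imputed as failures, so that disposition and the primary analysis contradict each other. An Early Withdrawal visit includes sigmoidoscopy if the previous one was more than 4 weeks before (Protocol 1.3.1). Week 12 is the first scheduled post-baseline endoscopy, so under SAP 3.2 and 8.5.1 a withdrawal endoscopy can be windowed to Week 12. A last dose on Day 57 is 85 − 57 = 28 days before Day 85, so the discontinuation rule in SAP 8.1.4, which needs more than 28, is not met with Day 85 as the timepoint.
- A reader might take Day 57 as a withdrawal day. It is a last-dose day. Someone who stops treatment on Day 30, has Follow-up on Day 58 and withdraws on Day 70 is correctly a non-completer.
- A reader might expect the effect to differ by arm, if subjects stopping for adverse events attend Follow-up more often. Nothing in the documents shows this.

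**Conclusion.** The point holds as a defect in one reported count. Followed literally, SAP 5.1.1 classes as a Week 12 completer any version 2.0 subject who withdraws without a Week 12 visit, has a last dose on Day 57 or later (Day 50 to 60 across the Follow-up window) and attends Follow-up. The threshold is plain date arithmetic. Including Follow-up is the natural reading of the SAP, not an express statement in it.

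The size depends on unknown withdrawal timing and Follow-up attendance. Under the stated assumptions, a true 8% is reported as 5.3% at full attendance, 6.7% at half and 7.3% at a quarter. The 5.3% is the full-attendance extreme for a 28-day Follow-up, not an expected value. Subjects lost to follow-up and those who consented only to version 1.0 are not affected.

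No primary or secondary efficacy result changes, because endpoint status does not use the disposition class. The power calculation and the on-treatment completion line are also unaffected.

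**What to change.** In SAP 5.1.1, replace the reference to the last assessment date with: *the date of the subject's last PCP assessment, excluding the PCP Follow-up visit*. State that a date on or after the comparator counts as complete. The PCP withdrawal date is an acceptable alternative, provided it is defined so that a later safety visit cannot move it. State that the same status determines Week 12 withdrawal in SAP 7.4 and 9.1.

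The cost is one phrase, a cross-reference and one programming condition, with no effect on alpha, power or study conduct. The only downside is a slightly less favourable reported Week 12 completion rate.
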